### 5.7.2 Statistical Analyses

Analyses will be conducted by the lead biostatistician in collaboration with resources from the Coordinating Site Committee (see above).

**Demographics:** All unit level and patient level categorical demographic information will be summarized on table 1 as proportions and frequencies. We will output all continuous data using mean plus standard deviation or median plus range.

**C. difficile acquisition Rate:** Acquisition rates will be obtained from each unit and comparisons for differences between control and intervention units using a chi-squared test. We will conduct a crude and adjusted linear and logistic regression model to determine predictors of C.diff acquisition in patients. Additionally, we will model the incidence of C.diff acquisition for intervention and control patients using Poisson regression models and to determine the gloving impact.

**CDI Infection Rate:** For unit-level data, we will compare changes in CDI infection rates between the intervention and control units using the chi-squares test or Fisher's exact test with post-hoc pairwise comparisons. For patient-level data, infection rates will be modelled for specific time periods (during 3, 6, 9 and 12 months; or every 3 months of the study period [up to 24 months]) using incidence split modeling to determine the point of highest infection within each unit, with appropriate covariate adjustment. We will use the Royston's trend test to conduct a time-trend analysis for CDI infection rates for specific time periods (during 3, 6, 9 and 12 months; or every 3 months of the study period).

**Other HAI Rates:** All other rates between intervention and control units will be compared using chi-squared test or Fisher's exact test, with post-hoc pairwise comparisons. All incidence and risk analysis will be conducted using Poisson regression models with covariate adjustment. For specific time periods (during 3, 6, 9 and 12 months; or every 3 months of the study period), we will use incidence split modeling to determine the point of highest infection within each unit, with appropriate covariate adjustment. We will use the Royston's trend test to conduct a time-trend analysis on the monthly HAI (CAUTI and CLABSI).

**Length of Stay:** A weighted two-sample and paired t-test will be used to compare mean length of stay between the intervention and control units.

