**30-Day Mortality:** Using patient level data, we will conduct a 30-day survival analysis to determine the hazard of mortality for control and intervention units using a cox proportional hazards model with Kaplan Meier curves. Within each unit, a risk analysis will be conducted to

determine the predictors of 30-day mortality. Additionally, we will examine survival percentages at specific periods of the intervention period (i.e. 3, 6, 9 and 12 months; or every 3 months of the intervention period) using life tables and log-rank tests to determine at which points mortality was highest for each unit.

*Other clinical outcomes:* Rates of toxic megacolon and colectomy will be compared between intervention and control units using chi-squared test or Fisher's exact test, with post-hoc pairwise comparisons. All incidence and risk analysis will be conducted using Poisson regression models with covariate adjustment. For specific time periods (during 3, 6, 9 and 12 months), we will use incidence split model to determine the point of highest infection within each unit, with appropriate covariate adjustment. We will use the Royston's trend test to conduct a time-trend analysis on the monthly outcomes.

*Intervention Fidelity:* We will calculate the compliance rates for both the intervention and control units and compare them using a chi-squared test. We will conduct a univariate logistical regression model to determine the odds of compliance with respect to additional unit characteristics such as number of beds and location. Monthly compliance will be modeled using a time series graphing technique with trend analysis estimates.

*Isolation Days of Care:* Monthly aggregate data of isolation patients will be collected from infection control at participating sites which are collected as standard of care and we will estimate the days of care by multiplying this number by the average length of stay for the participating unit. We will make comparisons between the intervention and control groups using the analysis of variance (ANOVA).

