## 7.1 Privacy and Confidentiality

Participant confidentiality and privacy is held in the highest regard by all study team members. This confidentiality is extended to cover all clinical information and testing of biological samples. Therefore, the study protocol, documentation, data, and all other information generated will be held in strict confidence. No information concerning the study, or the data will be released to any unauthorized third party without prior written approval. No individual results/PHI will be disclosed; only coded or aggregate data will be analyzed and only aggregate group-level data will be reported. Published study results will not identify individual units or subjects.

All study staff are up-to-date on VA privacy and information security trainings, specifically in ethical conduct, confidentiality protection, review of medical records, mandated reporting, and other topics of human research protections (including the Health Information Portability and Accountability Act (HIPAA). New staff will not be permitted to access any study data until they have completed all relevant trainings. Privacy will be maintained by conducting discussions and assessments in private rooms.

Removal of access to research study data will be accomplished for study personnel when they are no longer part of the research team. The Information Security Officer, Privacy Officer, and Associate Chief of Staff for Research will be notified immediately of any actual or suspected data breach.

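### Secondary analyses in section 5.7.2 search for peak periods and mortality predictors unit by unit, and add undefined pairwise tests; none of these estimates the gloving effect or its change over time

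*Combined protocol and SAP*

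**What the plan says.** All the analyses at issue are in section 5.7.2 of the combined protocol and SAP, under 5.8 Data Analysis.

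- **CDI and other HAIs.** Rates are compared between intervention and control units; for CDI this is done "using the chi-squares test or Fisher's exact test with post-hoc pairwise comparisons". Period-by-period incidence split models follow, used "to determine the point of highest infection within each unit". The periods are 3, 6, 9 and 12 months, or every 3 months (for CDI, up to 24 months).
- **Toxic megacolon and colectomy.** After a comparison of intervention with control units, "we will use incidence split model to determine the point of highest infection within each unit". Only the four periods to 12 months are named.
- **30-day mortality.** A Cox model compares control and intervention units. Two further steps are per unit. For predictors of death, the text reads "Within each unit, a risk analysis will be conducted to" identify them. Survival by period is examined "using life tables and log-rank tests to determine at which points mortality was highest for each unit".
- **Time trends.** Royston's trend test is planned for CDI, HAIs and the other clinical outcomes. It is not said to be run by arm.

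The section gives no multiplicity rule for these analyses and does not label them exploratory or descriptive. Section 7.1 (Privacy and Confidentiality) restricts reporting to aggregate group-level data and adds: "Published study results will not identify individual units or subjects".

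**The concern.** Randomisation supports one contrast per outcome: five gloving units against five control units, paired within site. The per-unit add-ons answer other questions.

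- A peak-period search always returns an answer, because one period must be highest (or tied) even if the true rate never changes. With few events per unit-quarter, that peak is mostly noise.
- For mortality the tool does not fit the task. A log-rank test asks whether survival curves differ; it does not identify the calendar period in which deaths were most frequent.
- Fitting predictors of death in ten units separately divides the deaths ten ways.
- Two arms give a single comparison, so pairwise comparisons after it must be of something else, and the text does not say what.

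The risk is that chance peaks and ordinary ward differences are over-read. Meanwhile the time question that matters for a behavioural intervention of up to 24 months goes unasked: whether the difference between arms grows or fades.

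**Working it through.** The plan states no figure for these secondary analyses, so there is nothing of its own to reproduce. The check asks what they would return if gloving had no effect and rates were constant.

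**Inputs from the documents.** Section 5.7.1 (Sample Size Determination) gives 100 admissions per unit-month, a 5-day stay, 9,879 patient-days per arm and five units per arm. Section 5.2.1 gives one intervention and one control unit at each of five sites.

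**Assumptions.** The documents give no CDI rate; 0.5 to 1.0 per 1,000 patient-days is assumed. Counts are taken as Poisson.

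**1. Chance peaks**
- Patient-days per unit-quarter: 100 × 5 × 3 = 1,500.
- Expected cases per unit-quarter: μ = 1,500 × 0.5/1,000 = 0.75, up to 1,500 × 1.0/1,000 = 1.5.
- Mean of the largest of K independent Poisson counts: Σ over k ≥ 0 of [1 − F(k; μ)^K], where F is the Poisson distribution function.

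| Expected per quarter | Quarters | Mean of highest | Ratio to true rate |
|---|---|---|---|
| 0.75 | 4 | 1.67 | 2.2 |
| 1.5 | 4 | 2.81 | 1.9 |
| 0.75 | 8 | 2.13 | 2.8 |
| 1.5 | 8 | 3.41 | 2.3 |

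In simulation, 32% to 45% of units also had a tied peak. The patient-level data cover consenting patients only (section 5.6), so actual counts would be lower and these ratios higher.

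**2. Pairwise comparisons, if they are between units**
- Pairs: 10 × 9 / 2 = 45, of which 5 are the randomised within-site pairs.
- Nominal false positives at a true 5% level: 45 × 0.05 = 2.25.
- An exact conditional test of two Poisson counts falls below its nominal level when counts are small. With 12,000 patient-days per unit (500 × 24), expected counts are 6 to 12 and the test rejects in about 2.4% to 3.0% of pairs. Then 45 × 0.024 = 1.1 and 45 × 0.030 = 1.35, or about 1.1 to 1.4 false positives per outcome with identical units.
- The chance of at least one is about 40% to 46% with the exact test. A normal-approximation test gives 55% (rate 0.5) to 63% (rate 1.0). The independence formula, 1 − 0.95^45 = 90%, overstates it because the pairs share units.

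**3. Mortality predictors in each unit**
- Patients per unit: 9,879 / 5 units / 5 days = 395, up to 100 × 24 = 2,400 if every admission over 24 months were included. The upper end is a ceiling, because only consenting patients have patient-level data.
- At an assumed 3% to 5% mortality, deaths per unit run from 395 × 0.03 = 12 to 2,400 × 0.05 = 120.
- If all 28 patient characteristics that can be counted in section 5.6 were candidates (an assumption, since the plan names none), there would be 12/28 = 0.4 to 120/28 = 4.3 deaths per candidate in each unit. Pooled over ten units the figures are about 4 to 43.

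**The case against.** **Each affected outcome has an arm-level comparison.** This stands. A reader might infer that the secondary outcomes are analysed by unit in place of by arm. The text does not support that: CDI, other HAIs, toxic megacolon and colectomy, and mortality are each compared between intervention and control units. The per-unit work is additional.

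**Chance results need not be reported as findings.** A reader might infer that unit peaks will be published as evidence about gloving. No section says so, and section 7.1 cuts against it by limiting reports to aggregate data, although coded unit results are not clearly excluded. What remains is that the plan specifies unit-level analyses whose results it can largely not report.

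**The pairs may not be units.** This also stands. A reader might take the 45 unit-against-unit tests as planned. The documents do not define the pairs, and periods or the five within-site pairs are possible. The defect in the text is the missing definition; the 45-test figures are conditional on one reading. It is also tempting to add that about 4 of 45 tests would be significant under modest ward variation. That figure needs assumed between-site and between-unit spreads, and the wards would then truly differ, so those results would not be false positives.

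**Describing peaks is ordinary infection-control work.** Fair, and it could help to interpret the monthly fidelity data. That supports keeping the peaks as labelled description, not as the stated target of a model or test.

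**Time is already covered.** Royston's trend test is planned, and the CDI paragraph speaks of comparing changes in rates. But neither is specified as an arm-by-period effect: the trend test is not stated by arm, and the comparison of changes is a chi-squared or Fisher test with no period term.

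**Conclusion.** The point holds for the add-on analyses. The peak-period searches and the mortality-predictor analyses are explicitly per unit and do not estimate the randomised contrast. The log-rank test does not suit the use given to it, and the pairwise set is undefined. The primary acquisition outcome and the planned arm comparisons of the secondary outcomes are not affected by this point.

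With no real change over time, the highest quarter in a unit would look 1.9 to 2.2 times the true rate over 4 quarters and 2.3 to 2.8 times over 8. This rests on the assumed CDI rate and the planning volume in section 5.7.1. If the pairwise tests are between units, they give about 1.1 to 1.4 false positives per outcome, against a nominal upper bound of 2.25. The sparse-data figures for mortality are weaker evidence, because both the death rate and the predictor list are assumed; that pooling gives ten times the deaths per predictor does not depend on either.

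**What to change.** In section 5.7.2:

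1. **Time.** Replace the per-unit peak and log-rank searches with an arm-by-period effect for each outcome, pooled over units, allowing for clustering by unit and pairing by site. At the assumed rates an arm would have 5 × 0.75 = 3.75 to 5 × 1.5 = 7.5 CDI cases per quarter. Wider periods, or a single linear trend in the arm difference, may therefore be needed, and the result should be presented as an estimate with its interval. Label any unit-level peaks that are kept as descriptive.
2. **Pairwise comparisons.** Delete them, or limit them to a descriptive display of the five within-site differences, with units coded in line with section 7.1.
3. **Mortality predictors.** Fit one pooled model stratified by unit in place of ten separate ones. Arm is constant within a unit, so this model cannot estimate the gloving effect; that stays with the Cox comparison of arms.

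The cost is a change of wording. No new data are needed, and there are fewer analyses in total. The loss is that unit-specific peaks and unit-specific predictor estimates are no longer inferential results.

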## 5.9 Withdrawal of Subjects

Sites that are unable to meet performance measures such as a) obtaining a high rate of stool samples from admitted patients and b) collecting primary and secondary endpoint data may be withdrawn from the study at the PI's discretion.

A unit may withdraw voluntarily from the study at any point. Attempts will be made to collect all data for the duration of their participation in the intervention phase regardless if they were unit randomized to the intervention or standard care group including 30-day mortality occurring after participant withdraw or termination.

Since there is a short data collection period of only 15 months, the study team does not plan to replace any units who withdraw or terminate.

## 6.1 Reporting

### 6.2 Adverse Events

Adverse event means any untoward medical occurrence associated with the use of an intervention in humans, whether or not considered intervention-related (21 CFR 312.32 (a)). An adverse event (AE) or suspected adverse reaction is considered "serious" if, in the view of either the investigator or sponsor, it results in any of the following outcomes: death, a life-threatening experience, inpatient hospitalization or prolongation of existing hospitalization, a persistent or significant incapacity or disability, or a manifestation of a congenital anomaly/birth defect. An AE is also considered serious when medical, surgical, behavioral, social, or other intervention is required to prevent an above outcome.

All AEs will be assessed by the PI using the following guidelines:

- **Mild** – Events require minimal or no treatment and do not interfere with the participant's daily activities.
- **Moderate** – Events result in a low level of inconvenience or concern with the therapeutic measures. Moderate events may cause some interference with functioning.
- **Severe** – Events interrupt a participant's usual daily activity and may require systemic drug therapy or other treatment. Severe events are usually potentially life-threatening or incapacitating. Of note, the term "severe" does not necessarily equate to "serious".

All adverse events (AEs) must have their relationship to study intervention assessed by the clinician who examines and evaluates the participant based on temporal relationship and his/her clinical judgment. The degree of certainty about causality will be graded using the categories below.

- **Related** – There is clear evidence to suggest a causal relationship, and other possible contributing factors can be ruled out.
- **Probably Related** – There is evidence to suggest a causal relationship, and the influence of other factors is unlikely.
- **Possibly Related** – There is some evidence to suggest a causal relationship (e.g., the event occurred within a reasonable time after intervention). However, other factors may have contributed to the event (e.g., the participant's clinical condition, other concomitant events). Although an AE may rate only as "possibly related" soon after discovery, it can be flagged as requiring more information and later be upgraded to "probably related" or "definitely related," as appropriate.
- **Unlikely to be related** – A clinical event, including an abnormal laboratory test result, whose temporal relationship to study participation makes a causal relationship improbable (e.g., the event did not occur within a reasonable time after administration of the trial medication) and in which other drugs or chemicals or underlying disease provides plausible explanations (e.g., the participant's clinical condition, other concomitant treatments).
- **Not Related** – The AE is completely independent of study participation, and/or evidence exists that the event is definitely related to another etiology. There must be an alternative, definitive etiology documented by the clinician.

All SAEs that are unexpected and related to the study will be reported by the study team to the

IRB in writing within 5 business days of the team becoming aware of the SAE. A specific reportable event form will contain a detailed description of the symptoms observed and the concomitant treatment administered. Furthermore, the report must comment on a possible causative relationship between the AE and the research procedures. Each SAE must be followed until it is resolved or can be explained satisfactorily.

Any death that is unanticipated and potentially related to the research will be immediately reported to the IRB by the study team.

### **6.3 Unanticipated Problems**

The Office for Human Research Protections (OHRP) considers unanticipated problems involving risks to participants or others to include, in general, any incident, experience, or outcome that meets all of the following criteria:

- Unexpected in terms of nature, severity, or frequency given (a) the research procedures that are described in the protocol-related documents, such as the Institutional Review Board (IRB)-approved research protocol and informed consent document; and (b) the characteristics of the participant population being studied;
- Related or possibly related to participation in the research (“possibly related” means there is a reasonable possibility that the incident, experience, or outcome may have been caused by the procedures involved in the research); and
- Suggests that the research places participants or others at a greater risk of harm (including physical, psychological, economic, or social harm) than was previously known or recognized.

Serious Problems that are both unanticipated and related to the research will be reported in writing within 5 days of becoming aware of the occurrence.

### **6.4 Protocol Deviations**

Protocol deviations from the VA Central IRB are considered an act of noncompliance. Protocol deviations must be reported within 5 days of being made aware of the occurrence if they are likely to substantially adversely affect any of the following:

- The rights, safety, or welfare of the research participant
- The participant's willingness to continue participation, or
- The integrity of the research data, including VA information security requirements

## 7.1 Privacy and Confidentiality

Participant confidentiality and privacy is held in the highest regard by all study team members. This confidentiality is extended to cover all clinical information and testing of biological samples. Therefore, the study protocol, documentation, data, and all other information generated will be held in strict confidence. No information concerning the study, or the data will be released to any unauthorized third party without prior written approval. No individual results/PHI will be disclosed; only coded or aggregate data will be analyzed and only aggregate group-level data will be reported. Published study results will not identify individual units or subjects.

All study staff are up-to-date on VA privacy and information security trainings, specifically in ethical conduct, confidentiality protection, review of medical records, mandated reporting, and other topics of human research protections (including the Health Information Portability and Accountability Act (HIPAA). New staff will not be permitted to access any study data until they have completed all relevant trainings. Privacy will be maintained by conducting discussions and assessments in private rooms.

Removal of access to research study data will be accomplished for study personnel when they are no longer part of the research team. The Information Security Officer, Privacy Officer, and Associate Chief of Staff for Research will be notified immediately of any actual or suspected data breach.

VA REDCap may be used for entering patient-level clinical data, unit-level clinical and observational data, patient surveys, and Environmental Service worker surveys. VA REDcap is a 21 CFR Part 11-compliant data capture system provided by the VA Information Resource Center. The data system includes password protection and internal quality checks, such as automatic range checks, to identify data that appear inconsistent, incomplete, or inaccurate. No individual identifiers will be entered into VA REDCap, and only authorized staff will have access to the study REDCap project(s). No other web applications and no mobile devices will be used in this study. Unless otherwise specified as part of a valid DUA, no data will be stored on computer hard drives and sensitive data will not be removed from the VA-protected environment at any time; thus, no data will be stored at an alternative (non-VA) site. Original electronic VA data will be backed up regularly and stored behind the VA firewall.

At the end of the study, all VA research data and information will be retained in accordance with the applicable VA Records Control Schedule (NARA RCS 10-1). Prior to any destruction of research records, the PI will contact the Records Management Officer for current policy. Records will be destroyed, when allowed by shredding (paper records) and/or in a manner from which they cannot be retrieved (electronic/digital records).

Additional security measures for specific study procedures are described below.

**Observations.** We will follow usual infection control practices for observations of intervention fidelity/barrier precaution compliance using an audit tool. No identifiable information regarding the healthcare worker or the patient will be recorded, and only aggregate data will be shared with each site.

**Interviews/Focus Groups.** Interviews of patients will be administered in patient rooms at the VA. Interviews/focus groups of healthcare workers will be conducted in private conference rooms and/or over the phone, with both parties in a private setting. Patient interviewers will undergo training around human subject's protection, the interview guide, and engaging patients in a sensitive, respectful manner that promotes patients' engagement in the interview.

Furthermore, interviewers will participate in role playing to prepare for interviews and an expert qualitative researcher will observe their first actual interviews. The importance of privacy and discretion will be emphasized to participants during the sessions.

Researchers will notify participants that they are recording. Participants will be asked not to identify their names or other identifying information during interviews. Audio files will only be labeled with a unique number will be generated for each patient and healthcare worker and linked to a different unique letter representing the hospital unit. This identifier will be for purposes of this study only and will not include individually identifiable private information. Data will be stored in a password-protected database and accessed only by approved research personnel via password-protected computers in locked offices. Only aggregate data will be analyzed and presented; patient-, worker-, or facility-specific data will not be identified.

The Centralized Transcription Services Program (CTSP), based at the Salt Lake City VA, will transcribe interviews/focus groups. The CTSP will remove all identifying information, such as name or other personal identifiers, from the transcript prior to analysis. An investigator will upload the tapes to a transcriptionist at CTSP. Multiple levels of security will ensure the integrity and confidentiality of all data stored on the system. The computer system operates entirely within the VA network, which is protected by firewalls maintained by the VA Central Office. Authorized study team members are assigned an active, individually unique user identification code and individually unique password. The accounts and passwords comply with existing VA policies and procedures for computer access. User identification codes limit access to specific directories and files. The computer system is accessed via computers assigned to authorized investigators. These computers are secured through use of individually unique user identification codes and passwords.

All audio files, field notes files, and transcript files will be stored and transferred within the VA network which is protected by firewalls maintained by the VA Central Office. Only approved study team members and transcribers will have access to the audio files. The recordings will be appropriately destroyed at the end of the study, and the coded transcripts will be maintained according to VA policy.

**Clinical Data Collection.** Only the local site and minimum Madison staff necessary for replacing individual identifiers in patient-level data with the study ID number will have access to patient information, for example, the code key connecting patient name with the study ID number. All remaining data transferred to the Madison VA, including stool samples, will be coded. Each participant will be assigned a unique study ID, and all research data will be coded with ID numbers only, not names or social security numbers. The document ("key") linking names and ID numbers will be stored in a separate password-protected document on a password-protected server, to which only essential study staff (LSI, RA, and Madison staff responsible for coding patient-level data) will have access.

Unless otherwise specified as part of a valid DUA, research data for purposes of statistical analysis and scientific reporting will be stored at the Madison VA hospital. All identifiable data will be stored in locked drawers/file cabinets in the Madison VA Research Office or on a secure, password-protected server space in a research folder accessible only to trained and approved study personnel. All research data will be de- identified (i.e., all personally identifying information will be removed) prior to transfer to external parties of a valid DUA, data analysis and manuscript preparation; all identifiers will be replaced by study ID. All documents and databases will be stored on a secure server behind the VA firewall, and housed within a password-protected folder only accessible to approved research team members (unless otherwise specified by a valid DUA).

We will work with sites to determine their preferred method of data collection/transfer; i.e., whether the Madison study team will download these aggregate data from the Corporate Data Warehouse or whether the local study team will upload these data to the Madison study team using VA-secure methods behind the VA firewall. Regardless of collection/transfer method, all data will be kept behind the VA firewall at all times unless otherwise specified in a valid DUA. No study data will be shared in a non- secure manner. All data will be shared in accordance with VA regulations and via methods approved by the required officials (e.g., as outlined in a Enterprise Research Data Security Plan signed by the CIRB Information Systems Security Officer). All culture samples will be sent to the coordinating site at the central microbiology research laboratory at the Wm. S. Middleton Memorial VA Hospital. No patient identifiers will be received by the central laboratory, and no individual results will be shared back with facilities.

